
1. Early recognition of patients needing specialist postoperative input
	
Royal College of Anaesthetists: Guidelines for the Provision of Anaesthesia Services 2019²⁵
 
 • Provision of Postoperative Care Recommendation 3.23: Mechanisms for the early recognition of patients requiring specialist postoperative input from geriatrician-led services and/or critical care should be developed. These should include patients at risk of or presenting with delirium, multiple medical complications, functional decline or complex discharge planning.

2. Postoperative intravenous iron therapy is indicated in patients with iron deficiency anaemia
	
International consensus statement on Postoperative Anaemia after Major Surgery 2018²⁶
 
 • Postoperative iron therapy: Should postoperative iron therapy be indicated, i.v. formulations are recommended

3. Extended pharmacological VTE prophylaxis is indicated in patients at high VTE risk after major abdominal or pelvic surgery
	
National Institute of Clinical Excellence: Venous thromboembolism in over 16s: reducing the risk of hospital-acquired deep vein thrombosis or pulmonary embolism (NG89) 2018
 
 • Consider extending pharmacological VTE prophylaxis to 28 days postoperatively for people who have had major cancer surgery in the abdomen.

Methods

1. Summary

A prospective, multicentre, study will be delivered by STARSurg Collaborative & EuroSurg Collaborative across Europe. Mini-teams of up to four collaborators (medical students and at least one doctor) per speciality group per data collection period will prospectively collect data over a continuous 14-day period at each participating centre. This will be on consecutive patients undergoing major abdominal surgery, with follow-up to 30 postoperative days. All mini-teams should be supervised by a consultant in surgery.

2. Study Aims:

- **Primary Aim:** To audit compliance to pre-, intra-, and postoperative audit standards in reducing risk of postoperative cardiovascular complication.

- **Secondary Aims**
 - To characterise rates and risk factors associated with postoperative cardiovascular complications following major abdominal surgery in Europe.
 - To explore the association of pre-operative and postoperative anaemia with postoperative cardiovascular complications and short-term outcomes (length of stay, readmission and 30-day mortality).

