 - To characterise the efficacy and safety profile of extended pharmacological thromboprophylaxis in patients at high risk for VTE.

3. Project Timeline:

- The suggested overall data collection periods will be Monday 24th January 2022 to 3rd April 2022. Each mini-team will collect data over a 14-day, consecutive period with subsequent 30-day follow-up:
 - Period 1: 00:00 24th Jan 2022 - 23:59 06th Feb 2022 (+ 30 Day Follow-up)
 - Period 2: 00:00 07th Feb 2022 - 23:59 20th Feb 2022 (+ 30 Day Follow-up)
 - Period 3: 00:00 21st Feb 2022 - 23:59 06th Mar 2022 (+ 30 Day Follow-up).
 - Period 4: 00:00 07th Mar 2022 - 23:59 20th Mar 2022 (+ 30 Day Follow-up).
 - Period 5: 00:00 21st Mar 2022 - 23:59 03rd Apr 2022 (+ 30 Day Follow-up).
- Patients should be included if their operation started (defined as 'knife-to-skin' time) within

the time period during the data collection periods as specified above.

- Additional data collection periods may be added later in the study, to give flexibility to include further centres, who have had logistical difficulties in study start up.
 - Period 6: 00:00 18th Apr 2022 - 23:59 01st May 2022 (+ 30 Day Follow-up).
 - Period 7: 00:00 2nd May 2020 – 23:59 15th May 2022 (+ 30 Day Follow-up).

4. Centre Eligibility:

- CASCADe is open to any hospital in UK and Europe that routinely performs either elective and emergency major abdominal surgery.
- All participating centres are required to register the CASCADe audit according to local regulations. In the UK, CASCADe has been confirmed by the NHS East of Scotland REC Committee that it does not need NHS ethical review under the terms of the Governance Arrangements for Research Ethics Committees (**Appendix F**).
- Internationally, individual study investigators are responsible for ensuring the correct audit, ethical or departmental approval has been achieved prior to commencing data collection (this can be registered as an audit, quality improvement project or service evaluation, if appropriate).
- Evidence of successful audit registration must be sent to study management team (or the appropriate regional lead for UK centres) prior to commencement of data collection. Centres will not be allowed to upload patients’ data onto REDCap without evidence of successful registration of the study.
- Following completion of the CASCADe audit, it is a requirement of participation that mini-teams should **present the audit findings** to the surgery and/or audit departments at each centre.

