 - Staged with a planned return for reoperation (such as but not limited to damage control laparotomy or burns surgery) OR
 - Change in operative plan such that during the first procedure it is determined that a reoperation is necessary, even if the patient was enrolled preoperatively
- **Return to theatre:** Each individual patient should only be included in the study *once*. Patients returning to theatre due to complications following earlier surgery can be included, as long as their indexed procedure has not already been included in the CASCADE audit.

You should collect data on consecutive patients operated at your centre during the data collection period. This means that all eligible patients should be included.

Strategies to identify consecutive eligible patients could include:

- *Daily review of elective theatre lists.*
- *Daily review of handover sheets/ emergency admission and ward lists.*
- *Daily review of theatre logbooks (both elective and emergency).*

6. Covariates:

Data will be collected on audit standards and confounding factors for risk-adjusted analyses. These include age, sex, ethnicity, body mass index, American Society of Anaesthesiologists (ASA) grade, relevant comorbidities, smoking status, anticoagulant or antiplatelet use, preoperative blood test values, and preoperative anaemia management. Variables including operative urgency, operative procedure, operative contamination, use of tranexamic acid, intraoperative blood transfusions used, haemoglobin level at transfusion, duration of procedure and post-operative iron therapy will also be collected. Without appropriately adjusting for risk factors, it is likely that any findings would be biased and unable to be appropriately analysed on a national scale. A full list of required data fields is available in **Appendix B**, and on the REDCap database.

7. Outcome Measures and Follow-up:

Primary outcome measure:

- Rates of compliance to pre-, intra-, and postoperative audit standards in reducing risk of postoperative cardiovascular complication.

Secondary outcome measures:

- Incidence of postoperative cardiovascular complications within 30-days of surgery according to the Standardized Endpoints for Perioperative Medicine (StEP) cardiovascular.¹³ (see **Appendix D: Definitions of Key Outcomes**).
- 30-day postoperative blood transfusion rates
- 30-day complication rates defined according to the Clavien-Dindo classification (see **Appendix D: Definitions of Key Outcomes**)

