Appendix A: Summary of data fields

Use with Appendix X (Data Dictionary) to aid data collection.

				REDCap Unique ID					
Section 1: Pre-operative data fields									
Age	___(years)	Gender	 Male  Female	ASA grade	 I  II  III  IV  V	BMI	___ . ___ (2dp)		
Smoking status	 Current (≤ 6 weeks)  Current (> 6 weeks)  Ex-smoker  Never smoked			Clinical Frailty Scale	 1-3  4-6  7-9	https://bit.ly/3c9ve3d			
Hx of cardiovascular disease (Tick all that apply)	 MI  Angina  TIA/stroke  Hypertension  Atrial Fibrillation  VTE  Pulmonary Embolism  Congestive Heart Failure (CHF) (If CHF: NYHA:  I  II  III  IV)			Hx of respiratory disease	 Exertional dyspnoea or CXR (mild COPD)  Exertional dyspnoea < 1 flight or CXR (moderate COPD)  Dyspnoea at rest/rate > 30 at rest or CXR (fibrosis or consolidation)  None	Hx of COPD	 Yes  No		
Hx of chronic kidney disease	 I  II  IIIa  IIIb  IV  None	Hx of liver cirrhosis	 Yes  No	Hx of diabetes mellitus	 Type I  Type II (diet / tablet / insulin?)  None	Active cancer and/or cancer treatment	 Yes  No		
IBD	 Yes  No			Hx of VTE	 Yes  No				

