Critical care admission	 No  Yes, planned from theatre  Yes, unplanned from theatre  Yes, unplanned from ward If yes, CVC inserted?  Yes  No	Critical care bed days	___ days	Postop Hb	 ___ g/L (day 0-1)  ___ g/L (day 1-3)  ___ g/L (day 4-6)  ___ g/L (prior discharge)  Not available	IDA mx (Tick all that apply)	 None  Iron supplementation  TXA  RBC transfusion (if RBC:  1  2  3  4  ≥ 5 units)		
30-day Follow-up									
Cardiovascular complications within 30 days (Tick all that apply)	 None		Bleeding complication within 30 days		 Clinical non-major bleeding  Major bleeding  None				
	 Myocardial infarction  Myocardial injury  Non-fatal cardiac arrest  Coronary revascularisation		Post-operative length of stay		___ days  None				
	 PE (symptomatic non-fatal / asymptomatic)  DVT (proximal / distal; if either symptomatic / asymptomatic)		Highest 30-day complication grade		___  I  II  III  IV  V (if V: Cardiac / PE / noncardiac?)				
			30-day Reoperation		___  Yes ___  No				
			30-day readmission		 No  Yes(planned/unplanned?)				

	 New onset AF  Stroke				If yes: what was grade of complication:  None  I  II  III  IV  V

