2. Critical care bed days (if yes)	Number (days from first post-operative day to day of discharge from critical care. If the patient has not been discharged prior to the end of 30-day follow-up, enter '31').	
3. Postoperative haemoglobin	Not applicable / Available (day 0-1, day 1-3, day 4-6, last prior to discharge) If available, please state value in grams/litre	
4. Postoperative interventions for anaemia	None / iron supplementation / Tranexamic acid / RBC transfusion (If yes: 1, 2, 3, 4, ≥5 units)	
5. Cardiovascular complications within 30 days	None / Myocardial infarction / Myocardial injury / Non-fatal cardiac arrest / Coronary revascularisation / Pulmonary embolism (symptomatic non-fatal / asymptomatic) / Deep venous thrombosis (proximal / distal; if either symptomatic / asymptomatic) / New onset Atrial fibrillation / Stroke (select all that apply) *see Appendix D for definitions Please indicate the POD of the event(s) selected.	• Clinical notes • PACS software
6. Bleeding complications within 30 days	None / Major bleeding / Clinically relevant non-major bleeding *see Appendix D for definitions	
7. Post-operative length of stay	Number (days between from the first post-operative day to day of discharge. If the patient has not been discharged prior to the end of 30-day follow-up, enter '31').	
8. Highest 30-day complication grade	None / Clavien-Dindo Grade I-V (see Appendix D for the full 7-point Clavien-Dindo scale). If grade V, was death cardiac, PE or non-cardiac? (see Appendix D for definitions)	
9. 30-day Reoperation	Yes / No	
10. 30-day Readmission	Yes - planned / Yes- unplanned / No (this applies if patient had died during initial admission) If yes: what is the grade of complication (none, grade I, grade II, grade III, grade IV, grade V)	
11. 30-day postoperative COVID status	None / Preoperative / Postoperative If preoperative: are you still symptomatic (yes/no) and were you vaccinated (no / partial / full)	
12. Haemoglobin on readmission	Not available / Available If available, please state value in grams/litre	
13. Interventions for anaemia at readmission	None / iron supplementation (Oral / Intravenous), blood transfusion (If yes: 1, 2, 3, 4, ≥5 units)	
14. Postoperative outpatient VTE prophylaxis duration	Number (days of pharmacological VTE prophylaxis the patient was discharged home with)	

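### Bleeding events carry no postoperative day in either appendix, so the safety of extended thromboprophylaxis cannot be assessed after discharge; the day of cardiovascular events is required in Appendix B but has no space on the Appendix A form

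*Protocol*

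**What the plan says.** Protocol section 2 lists as a secondary aim: "To characterise the efficacy and safety profile of extended pharmacological thromboprophylaxis in patients at high risk for VTE". Another secondary aim is "To explore the association of pre-operative and postoperative anaemia with postoperative cardiovascular complications and short-term outcomes".

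The data fields that serve these aims are in Appendix B, Post-operative Data Fields:

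- Field 5, cardiovascular complications: event types, followed by the instruction "Please indicate the POD of the event(s) selected".
- Field 6, bleeding complications: none, major, or clinically relevant non-major. No day is requested.
- Field 7, length of stay: days from the first postoperative day to discharge, entered as 31 if the patient is still in hospital when follow-up ends.
- Fields 14 and 15, prophylaxis: the number of days supplied at discharge, and the drug.
- Field 3, postoperative haemoglobin: "Available (day 0-1, day 1-3, day 4-6, last prior to discharge".

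The Appendix A form repeats these items. Its block headed "Cardiovascular complications within 30 days" consists of tick boxes without a day, and so does its bleeding block. The form opens with the direction "Use with Appendix X (Data Dictionary) to aid data collection". Section 6 says of the complete list: "A full list of required data fields is available in Appendix B, and on the REDCap database".

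**The concern.** Extended prophylaxis, as recorded here, starts when the patient goes home. Any judgement of its safety needs to know which bleeds came after that moment. Follow-up covers the whole 30 days from surgery, so a bleeding field without a day pools in-hospital bleeding with bleeding at home.

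In-hospital bleeding is unlikely to be a small nuisance in this population. The major-bleeding definition in Appendix D includes surgical-site bleeding that leads to re-operation, and fatal bleeding. Both can occur during the index stay. If such events enter the comparison, the exposure is charged with events that preceded it. The reverse path is equally plausible: a patient who bleeds early may be sent home without prophylaxis because of the bleed.

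For efficacy, the day of a venous thromboembolism (VTE) does the same work. A clot found before discharge may be the reason that the patient goes home on an anticoagulant. For the anaemia aim, the event day is needed to place a complication before or after a postoperative haemoglobin reading.

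**Working it through.** The plan gives no figure to reproduce. The check is a comparison of fields, followed by a short piece of algebra.

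**Which days are recorded**

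| Item | Appendix A form | Appendix B |
|---|---|---|
| Bleeding event | no day | no day (field 6) |
| Cardiovascular event, including VTE | no day | day required (field 5) |
| Discharge | length of stay | length of stay (field 7) |
| Prophylaxis after surgery | days supplied at discharge | days supplied at discharge (field 14) |
| Postoperative haemoglobin | windows | windows, last value undated (field 3) |
| Postoperative iron, tranexamic acid, transfusion | no day | no day (field 4) |

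The missing day on the form is unlikely to be a text-extraction fault, because other blanks in the same table (days of stay, haemoglobin values) came through.

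**What can be ordered**

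1. *VTE against discharge.* If the field 5 day is captured, comparing it with length of stay shows whether the event came before or after discharge. If collectors work from the form alone, the day may not be entered.
2. *Bleeding against discharge.* Neither appendix supplies the event day, so the comparison cannot be made even when every field is complete.
3. *Cardiovascular event against haemoglobin.* The event day gives a coarse ordering only. Two windows share day 1, and the last value before discharge is undated.
4. *Preoperative and intraoperative exposures.* These precede postoperative events by definition and are not affected.

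**What pooling does to the safety comparison**

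Let a be the risk of a bleed before discharge, and b the risk of a first bleed after discharge among those bleed-free at discharge. Use E for patients sent home with extended prophylaxis and N for those without. The safety question concerns b(E) against b(N). The field as written yields, in each group,

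observed risk = a + (1 − a) × b.

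When bleeds are uncommon, the observed difference is approximately

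[b(E) − b(N)] + [a(E) − a(N)].

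The second bracket is bias:

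- If an early bleed leads to prophylaxis being withheld, a(N) exceeds a(E), and prophylaxis looks safer than it is.
- If prophylaxis goes mainly to patients with larger operations, a(E) may exceed a(N), and it looks more harmful.
- If a(E) = a(N) = a, the risk ratio becomes [a + (1 − a)b(E)] / [a + (1 − a)b(N)]. This lies closer to 1 than b(E)/b(N), so a true excess is diluted.

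Patients who die before discharge cannot receive outpatient prophylaxis. If they stay in the comparison, every in-hospital fatal bleed falls in group N.

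The documents give neither a nor b, nor any distribution of event days, so no numerical size is offered.

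**The case against.** The best defence concerns the cardiovascular day. Appendix A is titled a summary and is meant to be read with the data dictionary, and section 6 locates the required fields in Appendix B and REDCap. The REDCap screens are not shown and may already hold the day. Collaborators must complete all fields, and data collection periods with more than 5% missing data are excluded. This largely stands. A reader might infer from the form that the cardiovascular event day is not collected, or that most events could not be placed before or after discharge. The documents support neither: Appendix B asks for the day, and nothing in the protocol shows how many would go unrecorded. What remains is a risk. The form carries fine detail elsewhere (symptomatic or asymptomatic embolism, named anticoagulants), so a collector has little reason to suspect an omission. Its pointer names an Appendix X although the dictionary is Appendix B, and section 8 has paper copies destroyed after upload. The hospital notes do remain.

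None of this answers the bleeding gap, because the governing appendix omits that day too. One could look to proxies: readmission, reoperation, or transfusion at readmission. Readmission carries a complication grade but no type, and reoperation has no date. A patient may also bleed in hospital and be readmitted for something else, or bleed at home without readmission.

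It could also be said that section 7 counts prophylaxis over the full 30 days, which would make in-hospital bleeds relevant. The fields, however, record only the outpatient course, and that is the part called extended.

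Finally, these are secondary, observational aims. That is true and limits the weight of the point. It is not a matter to leave to an analysis plan, because no analysis can use a day that was never collected.

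**Conclusion.** The point holds in two parts of unequal strength.

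- **Bleeding.** With every field completed as written, bleeds before discharge cannot be separated from bleeds during outpatient prophylaxis. The safety half of the thromboprophylaxis aim is open to bias whose direction cannot be known in advance. This rests on the two appendices as shown; it would fall only if REDCap holds a bleeding day that neither appendix mentions.
- **Cardiovascular events.** The appendices disagree, which puts at risk the day needed to place VTE relative to discharge and complications relative to the haemoglobin windows. The variable is specified, so this is a matter of reconciliation.

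A reader might go further and conclude that exposures and events in general cannot be ordered. That is too broad: preoperative and intraoperative exposures are unaffected, and the primary outcome does not use event timing. Nor would adding the day settle the anaemia aim completely, since postoperative anaemia treatments stay undated. The change should be made, but it concerns secondary aims only.

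**What to change.** 1. Add a postoperative-day entry for each bleeding event to Appendix B field 6, the Appendix A form and REDCap, and say how a second bleed in the same patient is to be recorded.
2. Add a postoperative-day entry beside each cardiovascular event on the Appendix A form, to match Appendix B field 5, and confirm that REDCap has it. Correct the form's reference to the data dictionary.
3. For the extended-prophylaxis analysis, start the comparison at discharge among patients discharged alive. Use event day against length of stay so that only VTE and bleeding after discharge count as outcomes. State how length of stay converts to the postoperative day of discharge and how an event on the discharge day is classed.
4. State as a limitation that postoperative iron, tranexamic acid and transfusion are undated and cannot be ordered against events.

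The cost is one extra number per event, needed only for patients who have one, with no change to care or follow-up. The post-discharge comparison will contain fewer events than the pooled one and so be less precise, but those are the events that bear on the question.

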- 30-day reoperation rates
- Critical care bed days up to 30 days postoperatively
- Length of in-patient stay (days) up to 30 days postoperatively
- 30-day readmission rates
- 30-day bleeding event rates (see **Appendix D: Definitions of Key Outcomes**)
- Length of pharmacological VTE prophylaxis (days) up to 30 days postoperatively.

Follow-up should be performed in line with current routine practice within each hospital settings. No additional telephone, in-person or questionnaire-based follow-up is required. Source data may be acquired from hospital in-patient notes, clinical electronic systems, or outpatient letters.

Prior to collecting data, all collaborators will be required complete the mandatory e-learning modules available from the CASCADE project online hub:
<https://incept.ac.uk/course/view.php?id=7>

These include: (1) CASCADE Patient selection; (2) Clavien-Dindo classification (3) Postoperative cardiovascular complications; (4) Postoperative bleeding complications; (5) VTE pharmacological prophylaxis; (6) Data safety governance; (7) Quiz

8. Data Governance:

Data will be collected and stored online through a secure server running the Research Electronic Data Capture (REDCap) web application,^{27,28} and allows safe anonymised data storage by collaborators across Europe. The service is managed by the Birmingham Surgical Trials Consortium (BiSTC) REDCap system hosted at the University of Birmingham, United Kingdom. The security of the study database system is governed by the policies of the University of

Birmingham. Data management and data security within the BiSTC REDCap will abide by the requirements of the General Data Protection Regulations (GDPR) and any subsequent amendments. Collaborators will be given secure REDCap project server login details, allowing secure data storage on the REDCap system.

No patient data will be uploaded or stored on the REDCap database without prior local permissions. All data should be handled in accordance with local data governance policies, and all paper copies of any data should be destroyed as confidential waste within the centre once uploaded to REDCap. Data collected during the CASCADE study can be used for future analyses at the Study Management Group's discretion.

9. Data Analysis & Sample Size:

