15. Postoperative outpatient VTE prophylaxis	None / Low molecular weight heparin / Direct oral anticoagulants / Warfarin *If DOAC was selected, was this dabigatran, rivaroxaban, apixaban, edoxaban or betrixiban?	
--	--	--

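### Inpatient VTE prophylaxis is not recorded and bleeding has no event day, so the 28-day standard rests on an unverified inference and the safety half of the extended-prophylaxis aim cannot exclude pre-discharge bleeds

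*Protocol*

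**What the plan says.** Section 7 (Outcome Measures and Follow-up) lists as a secondary outcome "Length of pharmacological VTE prophylaxis (days) up to 30 days postoperatively". The third post-operative entry under Audit Standards rests on the recommendation "Consider extending pharmacological VTE prophylaxis to 28 days postoperatively for people who have had major cancer surgery in the abdomen"; compliance with the standards is the primary outcome. Both clocks start at the operation. The third secondary aim in Section 2 is "To characterise the efficacy and safety profile of extended pharmacological thromboprophylaxis in patients at high risk for VTE".

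The form has two fields on postoperative prophylaxis, both for outpatients. In Appendix B, post-operative item 14 asks for "Number (days of pharmacological VTE prophylaxis the patient was discharged home with" and item 15 for the outpatient agent, "None / Low molecular weight heparin / Direct oral anticoagulants / Warfarin". Appendix A carries the same two fields. Neither appendix asks whether prophylaxis was given in hospital, when it began, or when it stopped.

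The events for the aim run over 30 days: "Incidence of postoperative cardiovascular complications within 30-days of surgery" on the efficacy side and "30-day bleeding event rates" on the safety side. Item 5 of Appendix B asks for the postoperative day of each cardiovascular event, including deep vein thrombosis and non-fatal pulmonary embolism. Item 6 offers only "None / Major bleeding / Clinically relevant non-major bleeding" and asks for no day. Fatal pulmonary embolism appears only in item 8, as a cause of a grade V event, again without a day. Item 7 records length of stay, entered as 31 if the patient is still in hospital at the end of follow-up.

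**The concern.** The duration outcome and the standard are defined on one clock and the data are collected on another. The part of the course that lies between the two, the inpatient days, has no field. One component of the primary outcome and one secondary outcome must therefore be inferred.

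The second issue is the order of exposure and event. Outpatient supply is decided at discharge, but bleeding is counted from surgery. A bleed in hospital may change what the patient is sent home with. Appendix D makes the link explicit, because a change in antithrombotic therapy, including stopping it, is one of the features that can qualify a bleed as clinically relevant. If such bleeds are counted against the supply that followed them, the comparison can show harm or protection where there is none. This is a data-capture gap: an analysis plan cannot use a date that was never collected.

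**Working it through.** **Plan's own figure.** The only computed number in the protocol is the sample size in Section 9: 300 centres × 10 patients per week × 2 weeks = 6000, which reproduces. Nothing below depends on it.

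**Duration.** Let L be length of stay (item 7) and D the days supplied (item 14). The values of L are chosen for illustration. Two patterns are compared:

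- Pattern A: prophylaxis on every inpatient day, 28 days in total, so D = 28 − L.
- Pattern B: no inpatient prophylaxis and 28 days supplied at discharge, so the days inside the 30-day window are min(28, 30 − L).

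| L | A: D recorded | A: L + D | B: days inside window | B: L + D |
|---|---|---|---|---|
| 3 | 25 | 28 | 27 | 31 |
| 5 | 23 | 28 | 25 | 33 |
| 7 | 21 | 28 | 23 | 35 |
| 10 | 18 | 28 | 20 | 38 |
| 14 | 14 | 28 | 16 | 42 |

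Item 14 alone understates pattern A by the whole stay. The sum L + D is exact for pattern A and overstates pattern B. The form cannot tell the patterns apart. Nor can it separate a patient with a 10-day stay, full inpatient cover and nothing supplied from one given no prophylaxis at all: both give L + D = 10 + 0 = 10. A patient still in hospital at day 30 has L = 31 and no discharge supply, so there is no record of prophylaxis either way.

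**Bleeding counted from surgery, exposure fixed at discharge.** Assume no true effect. Let r be the 30-day event risk, f the share of events before discharge, q the probability of extended supply without an earlier event, and q1 the probability after one. The documents give none of these.

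- Risk before discharge: p = r·f. Risk after discharge among those event-free: s = r(1 − f)/(1 − p).
- Share supplied: E = p·q1 + (1 − p)q.
- Risk if supplied: [p·q1 + (1 − p)q·s]/E.
- Risk if not supplied: [p(1 − q1) + (1 − p)(1 − q)s]/(1 − E).

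Take r = 0.02, f = 0.5, q = 0.3. Then p = 0.01 and s = 0.01/0.99 = 0.0101.

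- q1 = 0 (supply withheld after the event): 0.003/0.297 = 0.0101 against 0.017/0.703 = 0.0242, ratio 0.42.
- q1 = 0.6 (supply more likely): 0.009/0.303 = 0.0297 against 0.011/0.697 = 0.0158, ratio 1.88.
- q1 = q: ratio 1.00.

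With q = 0.3, r from 1% to 5% and f from 0.3 to 0.7, the ratio is 0.23 to 0.63 for q1 = 0 and 1.5 to 5.9 for q1 from 0.6 to 0.9. Counting only post-discharge events in patients event-free at discharge removes the artefact in this model.

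**Where that restriction is possible.**

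| Event | Day recorded | Can be placed before or after discharge |
|---|---|---|
| DVT, non-fatal PE (item 5) | yes | yes, with item 7 |
| Bleeding (item 6) | no | no |
| Fatal PE (item 8) | no | not in general |

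The item 5 request appears in Appendix B only; the Appendix A collection form shows no box for the event day.

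**The case against.** Much of the other side is sound. Length of stay is collected, so the day on which the discharge supply runs out can be derived. A reader might infer that total duration cannot be obtained at all, or that the 28-day standard is misclassified for everyone with more than a short stay. The protocol does not support that: nowhere does it say that item 14 alone is scored against 28 days, and a scoring rule may sit in an analysis plan not shown. If the standard is scored on the end date of supply, gaps in inpatient cover matter less. They still matter for the duration outcome, and for a standard about extending a course that is presumed to have started in hospital.

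A reader might also infer that the efficacy comparison is bound to be dominated by thromboses that came before the exposure. That does not follow either, because deep vein thrombosis and non-fatal embolism are dated and can be set aside. The risk ratios above are corner cases on assumed inputs, and they vanish if supply is unrelated to earlier events.

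The choice of time zero is ordinary analysis-plan content. Collectors also complete a training module on pharmacological prophylaxis whose content is not visible, so it is possible but not shown that treatment for a new thrombosis would be entered as prophylaxis. Item 10 helps slightly: a grade V complication recorded against a readmission places that death after discharge.

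None of this supplies a day for bleeding, or any record of inpatient prophylaxis.

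**Conclusion.** The point holds as a gap in data capture that should be fixed; it does not invalidate the study. It touches one of the nine listed audit standards, one secondary outcome, and mainly the safety half of one secondary aim.

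Duration and the 28-day standard can be approximated as stay plus supply, on the assumption of continuous inpatient cover that no field verifies. Where that assumption fails completely, a 7-day stay with 28 days supplied reads as 35 days although 23 fall inside the window. Patients in hospital throughout follow-up have no prophylaxis record.

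For bleeding, pre-discharge events cannot be separated by any analysis, and the resulting bias can go in either direction. Its size is unknown; the ranges shown rest on assumed event risks, timing and supply patterns. On the efficacy side the same problem is avoidable except for undated fatal embolism, and provided that the event day requested in Appendix B is actually collected.

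**What to change.** Add to Appendices A and B:

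- the first and last postoperative day of inpatient pharmacological prophylaxis, with a code for none given;
- the postoperative day of each bleeding event, and of death;
- an indicator of whether the discharge anticoagulant is prophylaxis or treatment.

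Show the item 5 event day on the Appendix A form as well.

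Define duration as inpatient days plus supplied days, counting none beyond day 30. For the pattern B example this gives 0 + min(28, 30 − 7) = 23. For the extended-prophylaxis aim, count thrombosis and bleeding from discharge, in patients alive and free of those events at discharge.

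The cost is about five short fields, taken from notes that collectors already review, and fewer events in the comparison because pre-discharge events leave it. Two limits remain. First and last day do not show interruptions between them. Because no extra patient contact is required, outpatient days will generally be days supplied rather than days taken. These changes concern recording and analysis only.
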